#### Other Data Collection, Measures, and Process:

A series of measures will be collected at the enrollment visit (V1), as well as at three post-intervention period visits for all participants. Those in the CCC group, who choose to receive HCC within 3 months, will also have an additional two post-interventions data collection visits.

#### Demographics:

Demographic information will include embedded elements to allow calculation of the Charlson Comorbidity Index Score (Charlson et al., 2008).

#### Autonomic cardiovascular Regulation [Blood Pressure (BP), Heart Rate (HR), Heart Rate Variability (HRV), Baroreflex Sensitivity (BRS), and Blood Pressure Variability (BPV)]:

Continuous BP and HR are acquired from noninvasive finger arterial pressure measurements and ECG for a minimum of 10 minutes in subjects lying down quietly, supine. Systolic BP and beat to beat, RR, intervals (RRI) files generated via the data acquisition system (BIOPAC acquisition system and software, Santa Barbara, CA) at 1000 Hz are analyzed using Nevrokard SA-BRS software (by Nevrokard Kiauta, d.o.o., Izola, Slovenia) for measures of BRS, HRV and BPV as follows: Frequency Method. Power spectral densities of SBP and RRI oscillations are computed by 512 points Fast Fourier Transform (FFT) and integrated over specified frequency ranges (LF: 0.04-0.15 Hz; HF: 0.15-0.4 Hz). A Hanning window is applied and the squared-coherence modulus is computed if coherence is >0.5 as reported. The square-root of the ratio of RRI's and SBP powers is computed to calculate LF, HF alpha indices, which reflect BRS (16). Power of RRI spectra in LF, HF range (LFRR and HFRR) are calculated in normalized units and the ratio of LFRR/HFRR is used as a measure of sympathovagal balance. Power of SBP spectra calculated as LFSAP is used as a measure of BPV. Sequence Method. BRS calculated by this method is based on quantification of sequences of at least three beats (n) in which SBP consecutively increases (UP sequence) or decreases (DOWN sequence), which are accompanied by changes in the same direction of the RRI of subsequent beats (n+1). The software scans the RRI and SBP records, identifies sequences, and calculates linear correlation between RRI and SBP for each sequence. If the correlation coefficient exceeds a pre-set critical value (0.85), the regression coefficient (slope) is calculated and accepted. The mean of all individual regression coefficients (slopes), a measure of sequence BRS, is then calculated for Sequence UP, DOWN and TOTAL. Time-Domain Analysis. Three time-domain parameters are used for hemodynamic variability. HRV is determined by computing the standard deviation of normal to normal intervals (SDNN), and the root mean square of successive beat-to-beat differences in R-R interval duration (rMSSD). BPV is the standard deviation of the mean arterial pressure (SDMAP).

#### HRV and BRS Data Processing and Interpretation:

Heart rate is measured as beat-to-beat intervals (RRI) recorded by pulse-wave recording, and will be analyzed using custom software developed by Matlab. Data can be loaded and viewed, and a subset of

the data can be selected to avoid artifacts during device placement or removal. Outlier identification is performed by determining all IBIs which demonstrate a 30% difference from the mean of the previous four samples. Such outliers are removed from the data set. HRV statistics that are generated include mean, variance, SDNN, rMSSD, VLF, LF, HF, TP, LF/HF, sample asymmetry, sample entropy, and coherence ("Heart rate variability: standards of measurement, physiological interpretation and clinical use. Task Force of the European Society of Cardiology and the North American Society of Pacing and Electrophysiology," 1996). All of the algorithms for computation of these parameters are derived from information or source code from the Physionet archive. Data are saved to Excel spreadsheets for further statistical analysis by study team members.

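### The plan gives two routes to rMSSD and SDNN, with different programs and only one stated interval-cleaning rule, and does not say which supplies the secondary endpoint

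*Combined protocol and SAP*

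**What the plan says.** The section Autonomic cardiovascular Regulation describes the recording: "Continuous BP and HR are acquired from noninvasive finger arterial pressure measurements and ECG for a minimum of 10 minutes". Systolic pressure and RR-interval files "at 1000 Hz are analyzed using Nevrokard SA-BRS software" "for measures of BRS, HRV and BPV as follows". HRV is then defined there as SDNN and rMSSD, and an LF/HF ratio is used for sympathovagal balance. The section gives no rule for cleaning the intervals. Its one correlation threshold concerns which baroreflex sequences count: "If the correlation coefficient exceeds a pre-set critical value (0.85), the regression coefficient (slope) is calculated and accepted".

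The section that follows, HRV and BRS Data Processing and Interpretation, states a method again: "Heart rate is measured as beat-to-beat intervals (RRI) recorded by pulse-wave recording, and will be analyzed using custom software developed by Matlab". After viewing, a subset of "the data can be selected to avoid artifacts during device placement or removal". Intervals that differ by 30% from the mean of the preceding four are removed. The listed output includes SDNN, rMSSD, LF, HF and LF/HF, saved to spreadsheets for the study team to analyse.

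The first item under Secondary Objectives names heart rate, SDRR, rMSSD, HF alpha and the Sequence measures, with no signal or program attached. Statistical Analysis says only that secondary outcomes are handled like the main comparison. Under Enrollment Visit, participants learn their group at V1. No section describes masking of the people who process the HRV files.

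**The concern.** Both sections are written as the method in force. Neither is called a backup, an exploratory step or a sensitivity analysis. The second is not simply a later stage of the first, because it restates the signal, the program and the measures. It also does more than supplement the first, because SDNN, rMSSD and LF/HF appear in both.

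An endpoint with two permitted values per woman is not fully specified. Whoever prepares the analysis file can see both results before deciding which to report. At the Matlab stage the operator may also decide which part of the recording counts, with no fixed window and no stated masking to group or visit. The plan expects rMSSD and SDRR to rise more with HIRREM, so the direction that would be favoured is known in advance. At stake is how far a between-group difference in these HRV measures can be trusted.

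**Working it through.** **1. The two routes side by side**

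| | Autonomic cardiovascular Regulation | HRV and BRS Data Processing and Interpretation |
|---|---|---|
| Signal | Finger arterial pressure and ECG; which one supplies the RR intervals is not stated outright | Pulse-wave recording |
| Program | Nevrokard SA-BRS | Custom Matlab software |
| Interval cleaning | None stated; the term normal-to-normal implies some exclusion | 30% rule against the preceding four intervals |
| Segment | At least 10 minutes recorded; no selection rule | Optional subset to avoid placement or removal artefacts |
| SDNN, rMSSD, LF/HF | Yes | Yes |
| HF alpha, Sequence BRS | Yes | Not listed |

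**2. Which endpoints are exposed.** Of the HRV and BRS parameters named in the first secondary objective, rMSSD has two routes. So does SDRR, if it means what the other two sections call SDNN. HF alpha and the Sequence measures have one route only.

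**3. Effect of choosing after seeing both results.** The plan states no figure for this and no alpha, so there is nothing to reproduce. Assume a two-sided 0.05 test and no true difference. Let Z1 and Z2 be the test statistics from the two routes for one measure, bivariate normal with correlation r. Then

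P(at least one significant) = 1 − P(|Z1| ≤ 1.96 and |Z2| ≤ 1.96).

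| r | False-positive rate | Excess over 0.05 |
|---|---|---|
| 0.99 | 0.057 | 0.007 |
| 0.95 | 0.065 | 0.015 |
| 0.90 | 0.070 | 0.020 |
| 0.80 | 0.078 | 0.028 |
| 0 (upper limit) | 1 − 0.95² = 0.0975 | 0.0475 |

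The documents do not give r. Both routes measure the same women at the same visits, so a high value is plausible, and 0.80 to 0.99 is the range used here.

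**4. Whether the routes could differ in practice.** This is an illustration on assumed inputs: simulated records of 700 beats at a mean interval of 850 ms (700 × 0.85 s = 595 s, about 10 minutes), 200 records per scenario. Unfiltered ECG intervals are compared with pulse intervals after the 30% rule.

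- No ectopic beats and no pulse timing error: identical (SDNN 25.6 ms, rMSSD 26.1 ms).
- Two ectopic beats, no timing error: rMSSD 51.7 ms unfiltered, 26.2 ms filtered.
- Five ectopic beats, no timing error: rMSSD 75.0 ms unfiltered, 26.3 ms filtered.

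The unfiltered figures are a worst case, because normal-to-normal implies that some beats are dropped. They show that the artefact rule alone can separate the two values, so it has to be stated for whichever route is used.

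**The case against.** The strongest reply is that this is a modest matter. The measures are secondary, the trial is a pilot meant to assess feasibility and effect size, and the inflation for one measure is a few percentage points at most. That stands, and it limits the weight of the point. It does not settle which value is the endpoint.

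A second reply is that the spreadsheet export in the Matlab section shows which output feeds the analysis. It is a hint, but it does not exclude the Nevrokard values, which the preceding section defines as the HRV measures.

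A reader might infer more than the documents support:

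- *That the routes measure different quantities.* Finger arterial pressure is itself a pulse wave, so the two sections may describe the same recording. Taking the Nevrokard intervals from the ECG is a reasonable inference, but it is not stated. If pulse intervals do carry beat-to-beat timing error of SD s, rMSSD becomes √(rMSSD² + 6s²): with an assumed s of 10 ms, √(26.1² + 600) = 35.8 ms. But s is not in the documents. The same route used throughout would inflate both arms, which might dilute a contrast but would not by itself favour HIRREM.
- *That two cleaning rules conflict.* Only the Matlab section states one for intervals. The coherence and correlation thresholds in the other section concern baroreflex measures.
- *That segments are freely hand-picked.* Selection is optional and tied to device placement and removal. What is missing is a fixed window and a masked operator.
- *That the HRV operators know the assignment.* Participants do. For operators the documents are silent.

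**Conclusion.** The point holds as an internal inconsistency with a selection risk. The plan states two methods for rMSSD and SDRR/SDNN in its first secondary objective and gives neither precedence. LF/HF is duplicated too, though that objective does not name it.

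The size, 0.057 to 0.078 per measure in place of 0.05, rests on an assumed alpha, the assumed correlation range and an analyst who reports the better result. It describes what the wording permits, not what anyone is expected to do. It does not include any further effect of operator-selected segments.

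A reader might also conclude that the trial's autonomic findings as a whole, or its main result, are in doubt. The documents do not support that: HF alpha and Sequence BRS are described by one route only, and the primary outcome comes from the hot flash diary. The plan should nevertheless be corrected, because the remedy is cheap and works only if it is made before the data are seen.

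**What to change.** Before any data are analysed:

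1. Name one signal and one program as the source of rMSSD and SDNN. Label the other route a sensitivity analysis, or limit it to measures that the first does not give.
2. Apply one stated artefact rule to the chosen route, for example the existing 30% rule. If Nevrokard is chosen, this has to be added, since otherwise the only stated cleaning rule would be lost.
3. Set one fixed rule for the analysed segment.
4. Process files under codes that hide group and visit.
5. Use one term, SDRR or SDNN, in all three places.

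This needs protocol wording and coded file names, with no new recordings. The downside is that a fixed segment rule may lose a few recordings that operator selection would have kept.

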#### Menopause -related symptoms:

Hot flash diaries provide a valid and reliable approach to understanding a participant's experience of hot flashes and night sweats (Sloan et al., 2001). An adapted hot flash daily diary that includes daytime and nighttime frequency and severity will be included. Categories are mild (1), moderate (2), severe (3), and very severe (4). Data will be used to calculate a hot flash severity score for each day as the sum number of hot flashes within each severity category multiplied by the severity score of that category, with the resulting sum divided by the total number of hot flashes. Participants will be asked to keep a 7-14 day daily hot flash diary after V1, and then 7-14 days before each subsequent data collection visit.

Hot Flash Related Daily Interference Scale (HFRDIS) is a 10 item measure to capture the daily impact of vasomotor symptoms in a variety of domains within the past week. These domains include work, social activities, leisure activities, sleep, mood, concentration, relation with others, sexuality, enjoyment of life, and overall quality of life. Items are scored from 1 (not at all) to 10 (extremely) (Carpenter, 2001).

The Menopause Rating Scale (MRS) is a survey that generates a score between 0 and 44 based on the individual's symptom severity rankings (Research, 2008). There are 11 symptoms listed related to perimenopause that are each assigned a score of 0 to 4 by the individual. A score of 0 indicates none, 1 is mild, 2 is moderate, 3 is severe, and 4 is very severe. After completion, the individual's score is tallied to create an overall score. Scores from 0-4 are considered zero to little, scores from 5-8 are considered mild, scores from 9-16 are moderate, and scores 17 or greater are considered severe.

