V1 to V2 between HCC and CCC, based on data from the hot flash daily diary. Following V3, those in the CCC group will be offered the opportunity to cross over to receive a course of HCC within 3 months, and will continue to be followed for data collections at 4-6 weeks (V4), and 12-14 weeks (V5) after completing their crossover HIRREM sessions. Additional mean contrasts will be constructed to evaluate the consistency of any benefit of HIRREM through subsequent visits beyond V3. Comparisons of changes in all secondary outcomes will be assessed in a similar fashion.

Importance: This study will explore the use of HIRREM for vasomotor symptoms associated with menopause in a randomized, clinical trial. The study will confirm feasibility using a closed-loop, acoustic stimulation intervention for a randomized clinical trial in this population, and will also provide estimates of effect size, which might justify larger controlled trials. A positive result would suggest that HIRREM might have benefit as a noninvasive, non-drug alternative for management of vasomotor symptoms. This, over and above the potential benefit from participating in a clinical trial, and interacting with the study personnel and the study environment. The study will also help to identify the characteristics of subgroups that might experience differential effects/benefits from HIRREM.

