High-resolution, relational, resonance-based, electroencephalic mirroring (HIRREM®) was developed by Brain State Technologies, Scottsdale, AZ. It is a commercially available, noninvasive, electroencephalic-based method to facilitate client-unique relaxation and auto-calibration of cortical neural oscillations by reflecting auditory tones in near real time (Gerdes, Gerdes, Lee, & Tegeler, 2013). HIRREM uses scalp sensors to observe brain frequencies and amplitudes in real time, and software-guided algorithmic analysis to identify and translate selected brain frequencies into audible tones to support real-time self-optimization of brain activity. The audible tones are reflected back to the recipient bilaterally, simultaneously, in 4-8 milliseconds, providing an opportunity for the recipient to, figuratively speaking, listen to the song the brain is playing right now. This rapid updating regarding its pattern allows the brain a chance to, self-optimize, self-adjust, “relax,” and reset/get unstuck from what has been stuck stress/trauma response patterns. The brain electrical patterns are typically observed to shift independently, with no conscious, cognitive activity required, no operant conditioning, and no learner in the loop, towards improved balance and reduced hyperarousal.

The mechanism of this effect remains to be fully understood, but may involve resonance between reflected tones and oscillating brain networks, much like a musical instrument tuning itself. Functionally, it may be that this acoustic stimulation facilitates kindling of sleep in neuronal units, which had previously been stuck in the “on” position due to stress responses (Krueger, Huang, Rector, & Buysse, 2013). Better sleep is foundational for all health and healing. A key aspect of observed beneficial effects may also be related to the observed improvement in downstream autonomic function, as evidenced by increased heart rate variability and baroreflex sensitivity, apparently associated with increased dynamic range and flexibility of autonomic responses managed by the brain.

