Table 2: Changes in clinical category for insomnia after HIRREM based on ISI scores

Clinical Category by ISI Score	Baseline (Percent of Total)	Post-HIRREM (Percent of Total)
No clinically significant insomnia (0-7)	2 (16.67%)	10 (83.33%)
Subthreshold insomnia (8-14)	4 (33.33%)	0
Moderate insomnia (15-21)	3 (25.00%)	2 (16.67%)
Severe insomnia (22-28)	3 (25.00%)	0

Figure 1 (A and B): Figure 1A: Changes in hot flash frequency over time. The Y-axis indicates hot flash frequency. The X-axis indicates the number of days since the start of the HIRREM sessions. Each colored line represents an individual participant in the study. Figure 1B: Changes in hot flash severity over time. The Y-axis indicates hot flash severity (1 = mild, 2 = moderate, 3 = severe, 4 = very severe). The X-axis indicates the number of days since the start of HIRREM sessions. Each colored line represents and individual participant in the study.

[figure not shown]
[figure not shown]

Figure 2 (A and B): Example of observed changes in brain electrical pattern. FFT spectral display of electroencephalic data with frequency (Hz, central Y-axis) plotted against transformed amplitude ( $\mu\text{V}$ , X-axis). Data represents one minute of data from the T3/T4 montage with EC at the baseline assessment (4-A), and at the penultimate minute of the final session (4-B) for one participant, a 47 year old woman. Note the change of amplitudes in the 23-36 Hz range (dark purple color), outlined by red boxes.

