##### Secondary Objectives:

Evaluate whether the addition of HCC to continued current clinical care will result in greater differential changes in a variety of physiological, behavioral, and function outcome measures outlined below, as compared to CCC.

[figure not shown]
1. Autonomic nervous system functions, as manifested by heart rate, HRV, and BRS. We expect to see greater changes in autonomic activity and an improvement of sympatho-vagal balance in the HCC group. This would be reflected as changes in heart rate, and an increase of HRV and BRS parameters such as the standard deviation of the R-R interval (SDRR), rMSSD, HF alpha, and Sequence Up, Down, or All.
2. Reduction in menopause-related scales: Menopause Rating Scale (MRS) and Hot Flash Related Daily Interference Scale (HFRDIS). We anticipate to see greater improvement in these symptoms in the HCC group.
3. Behavioral outcomes such as insomnia (assessed by the Insomnia Severity Index, ISI; Pittsburgh Sleep Quality Index, PSQI; and the Epworth Sleepiness Score, ESS), depression (as assessed by the Center for Epidemiological Studies-Depression Scale, CES-D), anxiety (as evaluated by the GAD-7), and stress (as assessed by the Perceived Stress Scale, PSS). We expect to see greater improvement in these symptom inventory scores in the HCC group.
4. Overall quality of life as evaluated using the QOLS. We hope to see greater improvement in overall quality of life scores in the HCC group.
5. Functional performance evaluated using drop stick reaction testing. We expect to see more improvement in the HCC group.
6. Functional performance evaluated by grip strength, using a hand dynamometer. We expect to see greater improvement of grip strength in the HCC group.

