### Overview:

[figure not shown]
This will be a randomized, single site, pilot clinical trial. Assuming a potential drop-out rate of 20%, up to 48 subjects will be enrolled to achieve a goal of having at least 40 subjects (20 per group) complete the study, per protocol. Patients who have at least 5 hot flashes per day (with at least one being categorized as moderate to severe) will be eligible to participate.

Those who have no other exclusions, are interested to participate, and provide informed consent will be randomly assigned to receive 8-16 sessions of in-office acoustic stimulation linked to brainwave activity (HCC), over a maximum of 4 weeks, while continuing their other current clinical care, or to continue their current clinical care alone (CCC). There will be pre- and post-intervention data collection to include a daily hot flash diary (to be completed for 7-14 days by both groups) and many secondary outcome measures including completion of the MRS, HFRDIS, measures of autonomic cardiovascular regulation (continuous recording of BP and HR for calculation of measure of HRV and BRS), behavioral symptom outcomes (ISI, PSQI, ESS, CES-D, GAD-7, PSS), quality of life measure (QOLS), and function performance measures (drop stick reaction testing, and grip strength). All measures will be collected at an enrollment visit (V1). Both groups will then maintain a hot flash diary for 7-14 days, after which the intervention will begin for the HCC group. Post-intervention data collections will include an intermediate post-intervention visit (V2, primary outcome, 4-6 weeks after intervention completion for HCC, and 10-12 weeks after V1 for CCC), and a final follow up visit (V3, 12-14 weeks following completion of the intervention for HCC, and 18-20 weeks after V1 for CCC). Both groups will maintain a hot flash diary for 1-2 weeks prior to the V2 and V3 visits. The primary outcome will be reduction in frequency and severity of hot flashes score from V1 to V2. Following V3, those in the CCC group will be offered the opportunity to receive a course of HCC within 3 months (will have another brainwave assessment 0-14 days before beginning sessions), and will continue to be followed for data collections at 4-6 weeks (V4), and 12-14 weeks (V5) after completing their HIRREM sessions.

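### The diary separates day from night but no analysis does, so part of a fall in whole-day hot flash frequency could be flashes slept through rather than fewer vasomotor events

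*Combined protocol and SAP*

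**What the plan says.** The Abstract (Methods) defines the primary outcome as the between-group difference in change in hot flash frequency and severity from V1 to V2, "based on data from the hot flash daily diary". The Overview puts it this way: "The primary outcome will be reduction in frequency and severity of hot flashes score from V1 to V2". Neither place mentions day or night.

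Under Menopause-related symptoms: "An adapted hot flash daily diary that includes daytime and nighttime frequency and severity will be included". The scoring rule that follows is for severity. Counts in each severity category are weighted by grade (1 to 4) and summed over the day, "with the resulting sum divided by the total number of hot flashes". No rule is given for frequency. The protocol names no objective flash monitor.

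On sleep, the Background suggests that "it may be that this acoustic stimulation facilitates kindling of sleep in neuronal units", while saying that the mechanism is not fully understood. Item 3 of the Secondary Objectives, which includes the three sleep inventories (ISI, PSQI, ESS), says: "We expect to see greater improvement in these symptom inventory scores in the HCC group". The section on HIRREM Sessions makes the number of sessions depend partly on self-reported sleep. The control group is a wait-list.

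The Statistical Analysis section does not mention hot flashes. Its primary test of efficacy is blood pressure from V1 to V3.

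**The concern.** A woman can enter a night-time flash in a diary only if she notices it, which mostly means being awake or being woken. How complete the night-time record is therefore depends on how well she sleeps, and the intervention is expected to change that in one arm. There is no sham arm to share the effect. If HIRREM improved sleep and left vasomotor activity unchanged, HCC women could still record fewer flashes at V2 than CCC women.

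With a single whole-day count, that result looks the same as a real vasomotor effect. The trial is meant to supply effect-size estimates that might justify larger studies, so the two explanations should be separable. The diary already holds the information needed, but the plan does not use it.

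**Working it through.** **Figures in the plan.** The documents give no day/night split, no SD of change and no power calculation, so there is no stated figure on this point to reproduce. What they give is:

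- Minimum baseline frequency: 5 flashes a day (Inclusion Criteria).
- Pilot median change in frequency: -2.32, range -14 to 3, n = 12 (Table 1).
- Pilot sleep: median change -8.5 points. Women with no clinically significant insomnia went from 2/12 = 16.67% to 10/12 = 83.33% (Table 2, which reproduces).
- Planned completers: 20 per group (Number of Subjects).

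**Size of the artefact for frequency.** Suppose the true vasomotor effect is zero. Let F be flashes per day, s the share at night, and m the extra fraction of night flashes that goes unnoticed in HCC. The spurious group difference is d = F × s × m. All three inputs are assumptions.

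| Case | F | s | m | d per day | d / 2.32 | Share of total (s × m) |
|---|---|---|---|---|---|---|
| Low | 5 | 0.20 | 0.10 | 0.10 | 4% | 2% |
| Mid | 7 | 0.30 | 0.25 | 0.525 | 23% | 7.5% |
| High | 10 | 0.40 | 0.50 | 2.00 | 86% | 20% |

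**Effect on a test of pooled frequency.** For a two-sided 5% normal test with 20 per group, SE = SD × √(2/20) and the rejection probability is Φ(d/SE − 1.96) + Φ(−d/SE − 1.96). The SD is also assumed. I take 2, 3 and 5.2, the last being a rough value from the pilot range (17 / 3.258 = 5.2).

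| Case | SD 2 | SD 3 | SD 5.2 |
|---|---|---|---|
| Low | 0.05 | 0.05 | 0.05 |
| Mid | 0.13 | 0.09 | 0.06 |
| High | 0.89 | 0.56 | 0.23 |

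For example, in the mid case with SD 2, SE = 0.632 and d/SE = 0.83, giving 0.13. For daytime frequency the term F × s × m drops out, and the rejection probability under no true effect returns to 0.05.

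**Severity.** The daily score is a mean per flash. Take 5 daytime flashes of grade 2 and 2 night flashes, one of which is then slept through:

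- Night flashes of grade 1: (10 + 2)/7 = 1.71 becomes (10 + 1)/6 = 1.83.
- Night flashes of grade 2: 14/7 = 2.00 stays at 12/6 = 2.00.
- Night flashes of grade 3: (10 + 6)/7 = 2.29 becomes (10 + 3)/6 = 2.17.

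The direction depends on the grade of the flashes lost, so no one-sided bias can be claimed for severity.

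**The case against.** **A flash slept through may be a real benefit.** The Abstract's objective and the Hypothesis speak of symptoms that women experience, and the diary is described as capturing the participant's experience of hot flashes and night sweats. On that reading, an unnoticed flash is one symptom fewer and the pooled count is right. This stands, and it is why the pooled count should remain primary. It does not license a claim of fewer vasomotor events, and the plan does not say which of the two it means to claim.

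**Pooling is not stated.** That is correct. The total in the scoring rule is the denominator of the severity score, and the frequency variable is never defined. Pooling is an inference from the whole-day score and the absence of any split. If it is not intended, the plan should say so.

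**The sleep evidence is weak.** The mechanism is offered tentatively, and the pilot was 12 uncontrolled women. The Abstract's Background also links vasomotor symptoms to poorer sleep, so better sleep could follow from fewer night flashes. In that case the night-time fall is genuine. This also stands. It is a reason to report night-time results alongside daytime ones, and not to discount them.

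**The benchmark is loose.** The -2.32 comes from women with a median baseline of 4.7 a day. Table 1 labels it as the final day of sessions, whereas V2 falls 4-6 weeks after the intervention. It gives scale only.

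A reader might go further and infer that the plan's primary result will be biased towards HIRREM, or that about half of the pilot effect is explained this way. The documents support neither. The direction holds for frequency only. A figure near half needs an unnoticed share at the top of the assumed range: 7 × 0.3 × 0.5 = 1.05, or 45% of 2.32.

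**Conclusion.** The concern holds in a limited form. Night-time frequency is recorded only when noticed, sleep is expected to improve more in HCC, the control is an unshammed wait-list, and no planned analysis separates day from night. Part of a fall in whole-day frequency could therefore reflect better sleep and not fewer vasomotor events.

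The size cannot be determined from the documents. Under the assumptions above it ranges from negligible (0.1 a day) to large (2.0 a day), with a mid case of about 0.5. The conclusion rests on two inferences: that frequency will be counted over the whole day, and that better sleep reduces noticing. It does not extend to the severity score, and it does not show that an observed effect would be spurious. It shows that the plan, as written, could not tell the two explanations apart.

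**What to change.** 1. In Menopause-related symptoms, define the frequency variable, state how day and night are delimited in the diary, and keep the pooled count as primary.
2. In Statistical Analysis, first reconcile the primary test (blood pressure, V1 to V3) with the hot flash outcome from V1 to V2. Then pre-specify daytime frequency from V1 to V2 as a supportive analysis, using the same between-group model as the pooled hot flash outcome. Report night-time frequency separately. Give estimates and confidence intervals for both.
3. State that the pooled result concerns flashes experienced. State also that a claim of fewer vasomotor events beyond better sleep rests on the size and confidence interval of the daytime contrast. Agreement in sign is not enough: with no daytime effect, the estimate would point in the favourable direction about half the time.

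The cost is one more run of the same model for each part of the day, on data the diary already collects, with no added visits or participants. Daytime counts are smaller (60-80% of the total under the assumed night share) and less precise. They may also shift slightly if longer sleep shortens waking hours, so the daytime contrast is a better guide to vasomotor events but not a perfect one.
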